8.2. Subject Disposition and Analysis Set Assignment

Subject disposition and analysis set assignment will be listed.

A summary table will be provided, based on the all subjects analysis set.

8.3. Screening Demographics

The screening demographics including age, sex, race, ethnicity, height, body weight, and body mass index will be listed.

A summary table will be provided, based on the safety analysis set.

8.4. Prior and Concomitant Medication

Prior medication will be defined as medication that ends prior to the first dose. Concomitant medication will be defined as medication that starts after dosing or starts but does not end prior to dosing.

Prior and concomitant medications will be coded using the World Health Organization Drug Dictionary (WHODrug) Global, Format B3, Version Month 2020 (or later if upversioned during the study). Prior and concomitant medications will be listed.

8.5. Pharmacokinetic and Pharmacodynamic Assessments

8.5.1. Pharmacokinetic Analysis

The following PK parameters will be determined where possible from the serum concentrations of AMG 890 using non compartmental methods in validated software program, Phoenix WinNonlin (Certara, Version 8.1 or higher):

The following parameters for OM will be summarized and listed:

Parameter	Units ^a	Definition
AUC _{last} ^b	h*ng/mL	area under the serum concentration-time curve from time 0 to the time of last quantifiable concentration (t _{last})

AUC _{inf} ^b	h*ng/mL	area under the serum concentration-time curve from time 0 extrapolated to infinity
C _{max}	ng/mL	maximum observed concentration
t _{max}	h	time to maximum observed concentration
t _{1/2}	h	apparent terminal elimination half-life
CL/F	L/h	apparent total body clearance
V _z /F	L	apparent volume of distribution during the terminal elimination phase
%AUC _{extrap}	%	percentage of AUC due to extrapolation from the last quantifiable concentration to infinity

^a Units are based on concentration units (provided by bioanalytical lab) and dose units used in the study.

^b AUCs will be calculated using the linear trapezoidal linear interpolation rule.

Additional pharmacokinetic parameters may be determined where appropriate.

Pharmacokinetic analysis will, where possible, be carried out using actual blood sampling times post dose. If actual times are missing, nominal times may be used with sponsor approval.

C_{max}, and t_{max} will be obtained directly from the concentration-time profiles. If C_{max} occurs at more than 1 timepoint, t_{max} will be assigned to the first occurrence of C_{max}.

8.5.1.1. Criteria for the Calculation of an Apparent Terminal Elimination Rate Constant and Half-Life

The start of the terminal elimination phase for each subject will be defined by visual inspection and generally will be the first point at which there is no systematic deviation from the log-linear decline in concentrations.

The apparent terminal elimination rate constant (λ_z) will only be calculated when a reliable estimate can be obtained using at least 3 data points, preferably not including C_{max}, and the coefficient for determination of exponential fit (R²) of the regression line is ≥ 0.8 . Parameters requiring λ_z in their calculation (eg, AUC_{inf}, %AUC_{extrap}, t_{1/2}, CL/F, and V_z/F) will only be calculated if the R² value of the regression line is ≥ 0.8 .

The following regression-related diagnostic PK parameters will be determined:

Parameter	Units	Definition
λ_z	1/h	apparent terminal elimination rate constant
λ_z Upper	h	end of exponential fit
λ_z Lower	h	start of exponential fit
λ_z N	NA	number of data points included in the log-linear regression
λ_z Span Ratio	NA	time period over which λ_z was determined as a ratio of t _{1/2}
R ²	NA	coefficient for determination of exponential fit

Where possible, the span of time used in the determination of λ_z (ie the difference between λ_z Upper and λ_z Lower) should be ≥ 2 half-lives. If the λ_z Span Ratio is < 2 , the robustness of the $t_{1/2}$ values will be discussed in the CSR.

Per Sponsor request, the half-life calculation is based on the beta phase of the elimination instead of terminal phase elimination. This decision is based on the PK properties of AMG890 where the terminal elimination phase constitutes a very small fraction of the total exposure (AUC) and the concentrations at terminal phase are close to the LLOQ value.

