AUC	area under the concentration-time curve
AUC _{inf}	area under the concentration-time curve from time zero to infinity
AUC _{last}	area under the concentration-time curve from time zero to time of last quantifiable concentration (t _{last})
BLQ	below the limit of quantification
CDISC	Clinical Data Interchange Standards Consortium
CI	confidence interval
C _{max}	maximum serum concentration
CL/F	apparent total body clearance
CSR	clinical study report
ECG	electrocardiogram
EOS	end of study
ICF	informed consent form
ICH	International Council for/Conference on Harmonisation of Technical Requirements for Registration of Pharmaceuticals for Human Use
λ _z	elimination rate constant
Lp(a)	Lipoprotein(a)
MedDRA	Medical Dictionary for Regulatory Activities
NC	not calculated
PD	pharmacodynamic
PK	pharmacokinetic(s)
R ²	correlation coefficient of terminal elimination phase
SAP	statistical analysis plan
SC	subcutaneous
SD	standard deviation
t _{1/2}	apparent terminal elimination half-life
TEAE	treatment-emergent adverse event
TFL	table, figure, and listing
t _{max}	time of maximum serum concentration
V _z /F	apparent volume of distribution during the terminal elimination phase
WHODrug	World Health Organization Drug Dictionary
%AUC _{extrap}	percentage of AUC that is due to extrapolation from the last measurable concentration to infinity

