8.5.1.2. Criteria for Calculation and Reporting of Area Under the Concentration-time Curve

The minimum requirement for the calculation of AUC will be the inclusion of at least 3 consecutive concentrations above the lower limit of quantification. If there are only 3 consecutive concentrations, at least 1 should follow C_{max} .

AUC_{inf} values where the percentage extrapolation is less than or equal to 20% will be reported. AUC_{inf} values where the percentage extrapolation is greater than 20% will be listed but flagged and excluded from descriptive statistics.

8.5.1.3. Criteria for Handling Below the Limit of Quantification or Missing Concentrations for Pharmacokinetic Analysis

Serum concentration values that are below the limit of quantification (BLQ) will be set to a value of zero, with the following defined exceptions which will be set to missing:

- Any embedded BLQ value (between 2 quantifiable concentrations).
- BLQ values following the last quantifiable concentration in a profile.
- If an entire concentration-time profile is BLQ, it will be excluded from PK analysis.

Where 2 or more consecutive concentrations are BLQ at the end of a profile, the profile will be deemed to have terminated and any further quantifiable concentrations will be set to missing for the calculation of the PK parameters unless they are considered to be a true characteristic of the profile of the drug.

If a predose serum concentration is missing, it may be set to zero by default.

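### SAP 8.5.1 and 8.5.1.1 define half-life, λz and Vz/F by the terminal phase but compute the half-life from the beta phase, and the 20% extrapolation exclusion in 8.5.1.2 stops at AUCinf

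*SAP*

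**What the plan says.** The parameter table in SAP 8.5.1 defines t1/2 as the "apparent terminal elimination half-life" and Vz/F as the "apparent volume of distribution during the terminal elimination phase". Section 8.5.1.1 gives the rule for choosing the regression window: "The start of the terminal elimination phase for each subject will be defined by visual inspection". It allows λz only when "a reliable estimate can be obtained using at least 3 data points, preferably not including" Cmax and R² is at least 0.8, and it names AUCinf, %AUCextrap, t1/2, CL/F and Vz/F as parameters that need λz. The diagnostics table there calls λz the terminal rate constant, and the abbreviation list glosses R² as the "correlation coefficient of terminal elimination phase".

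The closing paragraph of 8.5.1.1 then changes the phase: "Per Sponsor request, the half-life calculation is based on the beta phase of the elimination instead of terminal phase elimination". The reason given is that "the terminal elimination phase constitutes a very small fraction of the total exposure" and that concentrations in that phase lie near the LLOQ.

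On extrapolation, section 8.5.1.2 says that AUCinf values "where the percentage extrapolation is greater than 20% will be listed but flagged and excluded from descriptive statistics". It does not mention CL/F or Vz/F. Section 8.5.3 provides summary tables for every PK parameter except the regression diagnostics.

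**The concern.** The closing paragraph treats beta and terminal as two different phases, but no definition, label or window rule was changed to match. It speaks only of the half-life and does not say that λz, and everything computed from it, moves as well. A reader of the results would take the half-life and Vz/F for terminal-phase quantities when they are not. This matters for any comparison with the first-in-human study, which protocol 3.2 gives as a purpose of the trial.

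The extrapolation rule has a separate gap. CL/F is dose divided by AUCinf, and Vz/F follows from it. If an AUCinf is too extrapolated to summarise, so are these two. As written, the AUCinf row and the CL/F and Vz/F rows of one table can rest on different subjects in a group of about 12, and the latter rows keep the values built on the rejected AUCinf.

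**Working it through.** **Which phase feeds which parameter.** The standard noncompartmental identities are:

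- t1/2 = ln 2 / λz
- AUCinf = AUClast + Clast/λz
- CL/F = Dose / AUCinf
- Vz/F = (CL/F) / λz = (Dose / AUCinf) × t1/2 / ln 2

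Cmax and AUClast contain no λz. AUCinf and CL/F contain it only through the extrapolated part. Vz/F is directly proportional to the half-life used.

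The documents give no terminal half-life, so the following shows only where a change of phase would appear. It is not an effect size. Assume a two-phase profile with a beta half-life of 5 h (inside the 3 to 8 h in protocol 1.3), a slow half-life of 100 h, a slow phase of 5% of AUC, an LLOQ of 0.1% of Cmax, an absorption rate of 0.4/h and a dose of 1000 in arbitrary units:

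- Beta fit: t1/2 5.3 h, AUCinf 1029, CL/F = 1000/1029 = 0.972, Vz/F = 0.972 × 5.3/0.693 = 7.4.
- Terminal fit: t1/2 54.5 h, AUCinf 1038, CL/F = 1000/1038 = 0.963 (0.964 before rounding), Vz/F = 0.964 × 54.5/0.693 = 75.8 (75.7 before rounding).

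CL/F moves by under 1%, while Vz/F moves about tenfold with the half-life. Over 36 such scenarios (beta half-life 3, 5 or 8 h; assumed slow half-life 100 or 300 h, slow share 2, 5 or 10% of AUC, LLOQ 0.1 or 0.5% of Cmax), the terminal-to-beta ratio of Vz/F ran from 1.0 to about 87. AUCinf and CL/F differed by less than 5%. The spread in Vz/F reflects the assumptions.

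**When extrapolation exceeds 20%.** Assume one compartment with first-order absorption and elimination as the slower rate, so C(t) ∝ e^(−k·t) − e^(−ka·t). Half-life and tmax are taken within the 3 to 8 h ranges in protocol 1.3, which does not name the phase of the half-life. Then:

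extrapolated share = (Clast/k) / (AUC to tlast + Clast/k).

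Worked case: half-life 6 h gives k = 0.1155/h, and tmax 3 h gives ka = 0.730/h. With tlast 12 h, Clast = 0.2498, AUC to 12 h = 5.123 and Clast/k = 2.163. The share is 2.163/(5.123 + 2.163) = 29.7%.

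- tlast 12 h, tmax 3 h: 17.8% at half-life 4 h, and 20% is reached at 4.35 h.
- tlast 24 h: 20% is reached at half-life 9.9, 9.6, 9.2, 8.7, 8.0 and 7.2 h for tmax 3, 4, 5, 6, 7 and 8 h. Within the ranges only tmax above about 7 h with a half-life above 7.2 h crosses. The maximum is 22.2%.
- tlast 36 h: maximum 8.5%. tlast 48 h: maximum 3.1%.

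Repeating this with the linear trapezoid at the protocol's sampling times and the last three points after Cmax gives 30.6% for the worked case, and maxima of 25.7%, 10.2% and 3.2% at tlast 24, 36 and 48 h. The picture is the same.

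The early endings are demanding. In the worked case the 24 h concentration is still 10.5% of Cmax, and it would have to be below quantification for tlast to be 12 h. At the 4.35 h threshold it is 4.8%. For tlast 24 h with tmax 8 h, the 36 h sample would have to be unquantifiable at 15 to 17% of Cmax. In the 36 two-phase scenarios, extrapolation never exceeded 4.4%.

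**The case against.** The beta-phase paragraph is an explicit exception that closes the section holding the general window rule, and a specific exception governs a general rule. The SAP has only one rate constant, expresses the span of its fit as a ratio to t1/2, and lists t1/2 among the parameters that need it. The fit start, fit end, number of points and R² are determined for each fit, and section 8.5.3 lists all PK parameters, so the window used for each subject would be on record. %AUCextrap is itself listed and summarised, so an affected CL/F value could be traced.

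Most of this stands. It makes the single beta fit the natural reading and removes most of the doubt about what will be computed. It does not correct the definitions, which still describe a different phase, and it does not extend the 20% rule.

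A reader might go further and infer an undisclosed departure from the protocol, because SAP section 10 records no significant change. The documents give that little support: protocol 2.2.1 says only half-life, without naming a phase, and lists Vz/F among parameters that may be reported. Only the terminal wording of Vz/F there is at odds.

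**Conclusion.** The point holds as an inconsistency of definition and of rule. On the one-λz reading, half-life and Vz/F come from the beta phase under terminal-phase definitions, and CL/F and Vz/F can be summarised from an AUCinf that the SAP itself excludes. Both should be aligned.

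Two stronger inferences are tempting and not supported. One is that the primary PK results are compromised. Cmax and AUClast do not depend on λz, and AUCinf and CL/F should move little given the SAP's own statement that the terminal phase is a very small part of exposure. Half-life and Vz/F are additional parameters, and without a terminal half-life in the documents no size can be put on the difference. The other is that the summaries will contain many unreliable CL/F values. Under the stated half-life and tmax assumptions, the 20% case needs quantification to end at about 12 to 24 h. With sampling to Day 85 that is likely rare.

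The sponsor's preference for the beta phase is reasoned and is not in dispute. The TFL shells are not among the documents, so the table labels could not be checked.

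**What to change.** In SAP 8.5.1.1, state that one beta-phase regression supplies λz for t1/2, AUCinf, %AUCextrap, CL/F, Vz/F and the span ratio in all subjects, and reword the window rule so that it selects that phase. Label the rate constant, t1/2, Vz/F and R² as beta-phase in the parameter tables, the abbreviation list and the output. In 8.5.1.2, apply the exclusion above 20% extrapolation to CL/F and Vz/F as well as AUCinf, keeping the values listed and flagged. A line in section 10 on the beta-based Vz/F is optional.

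The cost is wording and labels. The noncompartmental analysis needs rerunning only if λz was fitted to a phase other than beta. The downside is that an occasional CL/F or Vz/F value leaves the summaries.

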8.5.1.2. Criteria for Calculation and Reporting of Area Under the Concentration-time Curve

The minimum requirement for the calculation of AUC will be the inclusion of at least 3 consecutive concentrations above the lower limit of quantification. If there are only 3 consecutive concentrations, at least 1 should follow C_{max} .

AUC_{inf} values where the percentage extrapolation is less than or equal to 20% will be reported. AUC_{inf} values where the percentage extrapolation is greater than 20% will be listed but flagged and excluded from descriptive statistics.

8.5.1.3. Criteria for Handling Below the Limit of Quantification or Missing Concentrations for Pharmacokinetic Analysis

Serum concentration values that are below the limit of quantification (BLQ) will be set to a value of zero, with the following defined exceptions which will be set to missing:

- Any embedded BLQ value (between 2 quantifiable concentrations).
- BLQ values following the last quantifiable concentration in a profile.
- If an entire concentration-time profile is BLQ, it will be excluded from PK analysis.

Where 2 or more consecutive concentrations are BLQ at the end of a profile, the profile will be deemed to have terminated and any further quantifiable concentrations will be set to missing for the calculation of the PK parameters unless they are considered to be a true characteristic of the profile of the drug.

If a predose serum concentration is missing, it may be set to zero by default.

8.5.1.4. Treatment of Outliers in Pharmacokinetic Analysis

If a value is considered to be anomalous due to being inconsistent with the expected PK profile, it may be appropriate to exclude this point from the PK analysis. However, the exclusion of data must have strong justification and will be documented in CSR.

Quantifiable predose concentration values in the first treatment period (if applicable) will be considered anomalous and set to missing for the PK analysis.

If the predose concentration is $>5\%$ of C_{max} in the second treatment period (if applicable), all PK concentration and parameter data may be excluded from the summary statistics and statistical analysis for that period at the discretion of the Pharmacokineticist.

8.5.2. Presentation of Pharmacokinetic Data

If the actual time of sample collection deviates from the nominal time by more than $\pm 20\%$, the concentration may be flagged and excluded from summary statistics. Individual concentrations that are deemed to be anomalous will be flagged in the listings and excluded from the summary statistics.

For PK concentration data the following rules will be applied:

- Values that are BLQ will be set to 0 for calculation of summary statistics.
- Arithmetic mean or median that are BLQ will be presented as 0.

For PK parameters the following rule will be applied:

- Geometric mean and coefficient of variation will not be calculated for t_{max} .

8.5.3. Pharmacokinetic Statistical Methodology

All PK concentrations and parameters will be listed.

Summary tables, mean (+ standard deviation [SD]) figures, overlaying individual figures, and individual figures by treatment group and time post dose will be provided for serum PK concentrations. All figures will be produced on both linear and semi-logarithmic scales. The $\pm SD$ bars will be only displayed on the linear scale.

Summary tables by treatment group will be provided for all PK parameters, with the exception of regression-related PK parameters. Separate summary tables by treatment group and time interval will be provided for excretion parameters.

8.5.4. Pharmacodynamic Statistical Methodology

Venous blood samples (approximately 6 mL) will be collected for measurement of Lp(a) at scheduled times.

Lipid panel will include triglycerides, very low-density lipoprotein cholesterol (VLDL-C), low-density lipoprotein cholesterol (LDL-C), and high-density lipoprotein cholesterol (HDL-C), total cholesterol, apolipoprotein A1 (ApoA1) and total apolipoprotein B (Apo B). At screening, lipid panel will measure triglycerides only. Venous blood samples (approximately 6 mL) will be collected for measurement of lipid panel at scheduled times. The lipid panel will be analyzed by a central lab of Covance Shanghai.

All PD parameters will be listed.

Summary tables and mean change and percent change from baseline (+ SE) figures by treatment and timepoint will be provided for all PD parameters based on PD analysis set.

Baseline is defined as the mean of last two non-missing values predose. If only 1 predose value is available then that value will be used as the baseline.

Values below the limit of quantification will be set to BLQ for the calculation of summary statistics.

Values recorded as $< x$, $\leq x$, $> x$, or $\geq x$ will be displayed in the listings as recorded. For the derivation of listing flags, calculation of summary statistics, and presentation in the figures, $< x$ and $\leq x$ values will be set to BLQ, whereas $> x$ and $\geq x$ values will be set to x .

No inferential statistical analyses are planned.

8.6. Safety and Tolerability Assessments

8.6.1. Adverse Events

All AEs will be coded using the Medical Dictionary for Regulatory Activities (MedDRA) Version 24.0 (or higher if upversioned during the study).

A treatment-emergent adverse event (TEAE) will be defined as any AE that starts on or after the first dose of investigational product (as determined by the flag indicating if the adverse event started prior to the first dose or not on the AE electric case report form) and up to EOS.

A treatment related TEAE will be defined as a TEAE with a relationship of possibly related or related to the study treatment, as determined by the investigator.

All AEs will be listed. In addition to the data recorded in the database, the listings will include derived onset time and duration. Onset time will be calculated from the time of dosing for TEAEs only.

The subject incidence of TEAE and the number of TEAEs will be summarized for the following categories based on safety analysis set:

- TEAEs (overall, serious, leading to study discontinuation, and leading to death) by treatment group
- TEAEs by severity and treatment group
- Treatment-related TEAEs (overall, serious, leading to study discontinuation, and leading to death) by treatment group
- Treatment-related TEAEs by severity and treatment group

The frequency of subjects will be summarized separately for TEAEs and treatment-related TEAEs events by the following:

- System organ class, preferred term, and treatment group
- Preferred term and treatment group

For the AE data the following rules will apply:

- For the derivation of TEAE status: If the start date/time of an AE is incomplete or missing, an AE will be assumed to be a TEAE, unless the incomplete start date/time or the end date/time indicates an AE started prior to the first dose.
- For the derivation of treatment-related TEAE status: If the study treatment relationship for a TEAE is missing, the treatment relationship will be kept as missing.
- For the derivation of onset time: If the start date/time of an AE is missing, onset time will not be calculated. If the start date/time of an AE is incomplete, where possible, the minimum possible onset time will be calculated and presented in ' \geq DD:HH:MM' format (eg, if the date/time of the last dose is 01MAY2019/08:00 and recorded start date/time of an adverse event is 03MAY2019, then the minimum possible onset time will be calculated by assuming the adverse event started at the first hour and minute of 03MAY2019 [03MAY2019/00:00], thus will be presented as onset time \geq 01:16:00 in the listing).
- For the derivation of duration: If the end date/time of an AE is missing, duration will not be calculated. If the start or end date/time of an AE is incomplete, where possible, the maximum possible duration will be calculated and presented in ' \leq DD:HH:MM' format (eg, if the start of an adverse event date/time is 01MAY2019/08:00 and its recorded end date/time is 03MAY2019, then the maximum possible duration will be calculated by assuming the adverse event ended at the last hour and minute of 03MAY2019 [03MAY2019/23:59], thus will be presented as duration \leq 02:15:59 in the listing).
- For the calculation of summary statistics: If the severity of a TEAE is missing, a TEAE will be counted as missing severity.
- For the calculation of summary statistics: If a subject experienced multiple TEAEs with the same preferred term for the same treatment group, this will be counted as separate TEAEs for that treatment under each specific severity recorded.

